### 3.3.2 TTNCS Measures

Threshold-tracking nerve conduction studies (TTNCS) is a neurophysiologic test for assessing lower motor neuron function. The following measures were obtained using standard procedures (Kiernan et al. 2000): strength-duration measures of strength duration time-constant (SDTC) and rheobase; threshold electrotonus measures of depolarizing threshold electrotonus at 40 to 60 ms [TEd (40-60 ms)], 90 to 100 ms [TEd (90-100 ms)], and at peak [TEd (peak)] and hyperpolarizing threshold electrotonus at 10 to 20 ms [TEh (10-20 ms)] and 90 to 100 ms [TEh (90-100 ms)]; recovery cycle measures of RRP, superexcitability, subexcitability after first pre-pulse, and subexcitability after second pre-pulse; peak amplitude measures of compound motor evoked potential (CMAP) and stimulus for 50% maximum response.

TTNCS tracings were centrally reviewed and processed. A central reader indicated the reliability of the overall TTNCS assessment and of individual measures using a set of quality flags. For primary analysis, all measures were excluded if the overall quality flag indicated that the full assessment was unusable. Otherwise, acceptable quality for primary analysis was separately indicated for peak amplitude (CMAP, stimulus for 50% maximum response), strength-duration measures (SDTC, rheobase), threshold electrotonus (TEd (40-60 ms), TEd (90-100 ms), TEd (peak), TEh (10-20 ms), TEh (90-100 ms)), RRP, superexcitability, and subexcitability (after first and second pre-pulse).

### **3.3.3 ALSFRS-R**

The ALSFRS-R (Cedarbaum et al. 1999) is a 12-item clinician-completed interview scale for assessing participants' function in four domains: bulbar, fine motor, gross motor, and respiratory. Each item is scored from 0 to 4 with higher scores indicating greater function. The ALSFRS-R total score is the sum of all items (range 0 to 48).

### **3.3.4 SVC**

Slow vital capacity (SVC) is the maximum volume of air that can be slowly exhaled after slow, maximal inhalation. Trained technicians coach participants through 3 to 5 maneuvers using a spirometer. The maximum volume expired is converted to percent of predicted normal. Normal values are calculated based on sex, age, and height using equations published by Knudsen et al. (1983).

### **3.3.5 APB Strength**

Bilateral abductor pollicis brevis (APB) muscle strength will be measured quantitatively by hand-held dynamometry (HHD) and assessed subjectively by manual muscle testing (MMT). MMT is a single 8-level item with scores ranging from 0 if no contraction can be achieved and 5 if the muscle exerts normal strength. Scores of 4 are subdivided into three levels ranging from 4- if active movement is achieved against the force of gravity and slight resistance to 4+ if active movement is achieved against the force of gravity and strong resistance.

### **3.3.6 Cramping**

Frequency of muscle cramping and maximum pain from muscle cramping is collected at baseline by retrospective report of the prior 7 and 30-day intervals. Prospective muscle cramping and pain from muscle cramping is recorded starting at baseline by participants in daily diaries and then summarized as weekly summaries of total number of cramps experienced and maximum and average daily maximum pain from muscle cramping.

### **3.3.7 Fasciculations**

Data on muscle fasciculations are captured at baseline and each post-baseline clinic visit by retrospective report of the prior 14-day interval. Data are captured on the experience of any fasciculations, the average duration of fasciculations, the association of fasciculations with exertion or times of rest, the degree to which fasciculations interfere with daily activities, and interference of fasciculations with sleep. Prospective data on fasciculations are recorded starting at baseline by participants in daily diaries and then summarized as weekly summaries indicating the number of days with no fasciculations, with fasciculations after exertion that did not substantially interfere with daily activities, with fasciculations at rest or after exertion that did

not substantially interfere with daily activities, and fasciculations that substantially interfered with daily activities.

### 3.3.8 AUA Symptom Score

The American Urological Association (AUA) Symptom Index (Barry et al. 2017) is a 7-item instrument addressing urinary frequency, nocturia, weak urinary stream, hesitancy, intermittence, incomplete emptying, and urgency. Each item is scored from 0 to 5 with higher scores indicating greater symptom severity. The AUA Symptom Score is the sum of all items (range 0 to 35). AUA Symptom Scores from 0 through 7 are classified as mild symptoms, scores from 8 through 19 are classified as moderate symptoms, and scores of 20 through 35 are classified as severe symptoms.

## 3.4 Determination of Sample Size

Caramia et al. (2000) report mean (SD) paired pulse SICI at 3 ms among 16 ALS patients of 125.7 (25.7) percent of MEP control size. Stefan et al. (2001) report paired pulse SICI at 3 ms among 13 ALS patients of 96.9 (35.9) percent of MEP control size. Assuming a mean (SD) equal to 100 (30) percent of MEP and using a two-sided alpha of 0.027 based on Dunnett's correction for comparing two treatments to placebo, 40 patients in each group and up to 25% loss to follow-up would give 80% power to detect a 25% difference between placebo and each active treatment based on a simple two-sample t-test. This accommodates the loss of power due to early stopping for futility and is conservative relative to our proposed shared-baseline mixed model analysis. For reference, Caramia et al. (2000) report an effect of three-week exposure to gabapentin equal to an 80% reduction of the paired pulse amplitude in untreated patients, and Stefan et al. (2001) report an effect of 5 or more day exposure to riluzole equal to a 35% reduction of the conditioned stimulus amplitude.

## 3.5 Analysis Samples

The following analysis samples will be used for testing safety, tolerability, and efficacy endpoints:

- Safety and Tolerability (ST) Sample: ALS participants who are eligible, randomized, and take at least one dose of study drug, classified according to the actual treatment received. Observations made after premature permanent discontinuation of study drug are included in this sample, should such participants remain on study.
- Efficacy Modified Intent-to-treat (mITT) Sample: ALS participants who are eligible, randomized, and take at least one dose of study drug, classified according to their randomized treatment assignment. Observations made after premature permanent discontinuation of study drug are included in this sample, should such participants remain on study.
- Efficacy Per-protocol (PP) Sample: ALS participants who are eligible, randomized, and take at least one dose of study drug, classified according to the actual treatment received. Observations made after premature permanent discontinuation of study drug (whether due to intolerance, early termination, loss to follow-up, or death) are excluded from this sample.

- Efficacy Low RMT (loRMT) Sample: ALS participants and observations in the PP sample with RMT less than 67% of maximum stimulator output. This criterion ensures that the full TMS input/output curve could be conducted.
- Efficacy All Quality (AllQual) Sample: ALS participants and observations in the PP sample with no restriction that TMS quality is good.

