### 5.2 Inclusion and Exclusion Criteria for ALS Subjects

#### 5.2.1 Inclusion Criteria

Study subjects meeting all of the following criteria will be allowed to enroll in the study:

1. Male or female, aged 18 to 80.
2. Sporadic or familial ALS diagnosed as possible, laboratory-supported probable, probable, or definite as defined by revised El Escorial criteria.
3. Slow vital capacity (SVC) measure  $\geq 50\%$  of predicted for gender, height and age at the Screening Visit, OR in the opinion of the SI, ability to perform and safely complete all study visit procedures.
4. Subjects must not have taken riluzole for at least 30 days, or be on a stable dose of riluzole for at least 30 days prior to the Screening Visit and continue on the stable dose throughout the course of the study (riluzole-naïve subjects are permitted in the study).
5. Subjects must be able to swallow oral medication at the Screening Visit and expected to be able to swallow tablets throughout the course of the study.
6. Capable of providing informed consent and following trial procedures.
7. Geographically accessible to the site.
8. Women must not be able to become pregnant (e.g., post menopausal, surgically sterile, or using adequate birth control methods) for the duration of the study and three months after study completion. Adequate contraception includes: abstinence, hormonal contraception (oral contraception, implanted contraception, injected contraception or other hormonal contraception, for example patch or contraceptive ring), intrauterine device (IUD) in place for  $\geq 3$  months, barrier method in conjunction with spermicide, or another adequate method.
9. Use of medications known to affect the neurophysiology measures in the study must be scheduled, not as needed (*pro re nata*, PRN). A subject must have been on a fixed dose for 30 days prior to the Screening Visit, and there must be no reason to believe that a subsequent change would be necessary during the course of the study. These medications include: benzodiazepines, muscle relaxants, tricyclic antidepressants, selective serotonin reuptake inhibitors, non-selective serotonin reuptake inhibitors, hypnotics (including anti-histamines) and anti-cholinergics.
10. TMS shows sufficient MEP amplitude and/or NCS studies show sufficient CMAP amplitude (amplitudes defined in MOP).

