#### **5.6. Reasons for Withdrawal**

A subject will be withdrawn from the study if:

- Any clinical AE, laboratory abnormality, concurrent illness, or other medical condition or situation occurs such that continued participation in the study would not be in the best interest of the subject. Note, however, that any subject who has initiated treatment should only discontinue study drug and remain on study if the safety concern relates to study drug and not to study procedures.
- The subject no longer meets eligibility criteria at any time prior to initiating study drug or is discovered at anytime to have been enrolled in error.

Subjects are free to withdraw from participation in the study at any time upon request.

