## 13 STATISTICAL CONSIDERATIONS

### 13.1 Analysis Populations

The unmatched healthy controls, matched healthy controls, and ALS subjects represent three distinct populations of individuals for the purposes of analysis. Some unmatched or matched healthy controls may be excluded from analysis if there is good reason to question their status as neurologically normal. All ALS subjects who are randomized and receive at least one dose of study drug will compose the modified intention to treat (mITT) population and will be included in primary analyses of safety, tolerability, and efficacy. For mITT analyses, subjects will be grouped according to their randomized treatment assignment regardless of treatment actually received or compliance with assigned treatment.

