## 1. Introduction

This Statistical Analysis Plan (SAP) defines the outcome measures and analysis samples and specifies the planned analyses of data from [name] Ezogabine trial. This SAP is specific to analysis of data related to the ALS participants in the randomized intervention trial. The SAP supplements the clinical protocol. Please refer to the clinical protocol for details on the rationale for the intervention, eligibility criteria, conduct of the trial, clinical assessments and the timing of their use in the trial, definitions and reporting of adverse events, data management conventions, and regulatory oversight and compliance procedures. In case of discrepancies between the SAP and the clinical protocol concerning matters of analysis, the SAP is authoritative. On all other matters, the clinical protocol is authoritative.

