### 2.3 Study Populations

Individuals eligible for trial participation as an ALS participant are men or women at least 18 years old who meet the El Escorial criteria of possible, laboratory-supported probable, probable, or definite criteria for a diagnosis of ALS and have a slow vital capacity (SVC) at least 50% of that expected based on age, sex, and height. Individuals eligible for study participation as an UHC participant are men or women at least 18 years old who do not have a history or family

history of possible motor neuron disease. Individuals eligible for study participation as a MHC participant are men or women who do not have a history or family history of possible motor neuron disease and are within 10 years of age of an enrolled ALS participant. Detailed inclusion and exclusion criteria are specified in the clinical protocol.

Participants will be recruited from a total of 12 clinical sites located through the US.

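### SAP 3.5 adds an undefined eligibility condition to the safety and mITT samples that Protocol 13.1 does not have; read literally, a dosed participant later found ineligible is in no analysis sample

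*SAP*

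**What the plan says.** SAP 3.5 defines five analysis samples. The safety sample is introduced as "Safety and Tolerability (ST) Sample: ALS participants who are eligible, randomized, and take at least one dose of study drug", with participants classified by the treatment they actually received. The primary efficacy sample is introduced as "Efficacy Modified Intent-to-treat (mITT) Sample: ALS participants who are eligible, randomized, and take at least one dose of study drug", classified by randomized arm. The per-protocol (PP) sample begins with the same three conditions. The loRMT and AllQual samples are both drawn from PP.

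Protocol 13.1 has two conditions, not three: "All ALS subjects who are randomized and receive at least one dose of study drug will compose the modified intention to treat (mITT) population". It adds that these subjects "will be included in primary analyses of safety, tolerability, and efficacy".

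SAP section 1 settles which text governs: "In case of discrepancies between the SAP and the clinical protocol concerning matters of analysis, the SAP is authoritative".

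Protocol 5.6 lists among the reasons for withdrawing a subject that the person "is discovered at anytime to have been enrolled in error".

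The samples matter because SAP 3.8.1 fits the primary model in mITT, SAP 3.2.2 uses the safety sample as the denominator for safety proportions, and SAP 3.9.1 summarizes treatment-emergent adverse events in that same sample.

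**The concern.** In SAP 3.5 the word *eligible* stands beside randomization and dosing as a condition of membership. The protocol's rule depends on facts fixed once the first dose is taken. The SAP's rule adds a condition whose answer may change later, and Protocol 5.6 expects that it sometimes will.

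Two things are at stake. In the efficacy sample, removing people after randomization departs from the randomized comparison and from the ITT principle invoked in Protocol 13.5. In the safety sample, the question is what happened to people who took the drug, and eligibility has no bearing on whether someone was exposed or had an event. Because PP carries the same condition as mITT, none of the sensitivity analyses listed in SAP 3.8.2 would show what the exclusion did.

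**Working it through.** **Step 1: set the definitions side by side.**

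| Sample | Eligible | Randomized | At least one dose |
|---|---|---|---|
| Protocol 13.1 mITT (safety, tolerability, efficacy) | not required | required | required |
| SAP 3.5 Safety and Tolerability | required | required | required |
| SAP 3.5 mITT | required | required | required |
| SAP 3.5 PP | required | required | required |
| SAP 3.5 loRMT, AllQual | inherited from PP | inherited | inherited |

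**Step 2: follow one participant through.** Take someone who is randomized, takes a first dose, and is then found to have been enrolled in error. Under Protocol 5.6 that person is withdrawn. This ends follow-up but does not cancel the data already collected. Under Protocol 13.1 the person is in mITT and contributes those data. Under the literal SAP 3.5 the person fails the first condition of ST, mITT and PP, and so cannot be in loRMT or AllQual. The SAP defines no all-treated sample that would pick the person up.

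**Step 3: reproduce the plan's sample size, to gauge the effect on power.** Inputs from SAP 3.4: difference δ = 25 points on a mean of 100, SD σ = 30, two-sided α = 0.027, 40 per group, up to 25% loss, 80% power, two-sample t-test.

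Power = P(|T| > t at 1 − α/2), where T is noncentral t with 2n − 2 degrees of freedom and noncentrality δ / (σ√(2/n)).

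- n = 28 evaluable per group: 79.8%
- n = 29: 81.4%, so 29 are needed; 29 / (1 − 0.25) = 38.7, rounded up to 39, against the 40 stated
- n = 40 × 0.75 = 30: noncentrality 25 / (30 × √(2/30)) = 3.23, power 82.8%

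The α also checks: with correlation 0.5 between the two comparisons, 0.027 each gives a familywise error of 0.0501. The plan's figure is reproduced.

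**Step 4: apply the extra condition.** The documents give no rate of late-found ineligibility, so the fraction f is an assumption, spread evenly over arms. Evaluable n per group = 40 × (1 − f) × 0.75.

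| Assumed f | Excluded of 120 | Evaluable per group | Power |
|---|---|---|---|
| 0 (protocol rule) | 0 | 30.0 | 82.8% |
| 1% | 1.2 | 29.7 | 82.4% |
| 2% | 2.4 | 29.4 | 82.0% |
| 5% | 6 | 28.5 | 80.6% |
| 10% | 12 | 27.0 | 78.2% |

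Power stays above 80% up to an assumed 5%. The consequence that matters is the one in Step 2.

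**The case against.** The best reply is that the word only describes the normal order of events. SAP 2.4 and 2.5 have participants found eligible and then randomized, and the same opening is used for ST, mITT and PP, so eligibility is not what separates PP from mITT. Neither document sets up a procedure for reviewing eligibility after dosing, and Protocol 5.6 is a withdrawal rule, not an analysis rule. This reading is fair and may be what was meant. It does not remove the point: SAP 3.5 does not say that eligibility is fixed at randomization, and if that was the intention the word is redundant and can go at no cost.

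Three stronger readings may tempt a reader and are not supported.

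- *Participants with low vital capacity would be dropped.* SAP 2.3 says participants "have a slow vital capacity (SVC) at least 50% of that expected based on age, sex, and height", while Protocol 5.2.1 also admits people on the alternative "OR in the opinion of the SI, ability to perform and safely complete all study visit procedures". But SAP 2.3 is a summary that leaves the detailed criteria to the protocol, and SAP section 1 refers readers to the protocol for eligibility. The Protocol Summary shortens the criterion in the same way. The full criterion in 5.2.1 governs, and people admitted under its alternative are eligible.
- *Exclusions would be made knowing the treatment.* SAP 2.7 blinds site staff, coordination and data management staff, the medical monitor and the clinical Steering Committee members to allocation. A blinded decision based on pre-randomization facts need not bias the comparison. What stands is that the SAP does not say who decides, when, or with what knowledge of a participant's course.
- *Adverse events would escape safety oversight.* Event recording, 24-hour reporting of serious events, medical monitor review and DSMB summaries (Protocol 11.2, 11.3 and 12.1) are not tied to the ST sample. The gap is confined to the SAP's analyses and tables.

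**Conclusion.** The point holds as a conflict between the two documents, in which the narrower and undefined rule prevails. Applied literally, it can remove a dosed participant from the primary efficacy model and from every safety summary based on the ST sample, with no other sample to show the omission.

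Its practical size is unknown. The documents report no such participant and give no rate. Under an assumed 1% to 5%, about 1 to 6 of 120 people would be affected, and power would move from 82.8% to between 82.4% and 80.6%. These figures rest on the plan's simple t-test and on 120 randomized. SAP 3.7 records slower enrollment than expected, so the number actually randomized may be lower. One excluded person is 1/40 = 2.5% of a planned arm's denominator; that is a share of participants, not an event rate.

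This is a wording fault of moderate weight. It is worth correcting because it touches both the primary efficacy sample and the only safety sample, and because the correction is nearly free. It is not evidence that the trial's results are biased.

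**What to change.** In SAP 3.5, delete *eligible* and its comma from the Safety and Tolerability and mITT bullets, so that membership rests on randomization and at least one dose alone, as in Protocol 13.1. Leave the classification rules (actual treatment for safety, randomized arm for mITT) as they are.

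If an eligibility exclusion is wanted, keep it in the PP sample only, where the word already stands. Add a sentence stating which criteria count, who decides, and that the decisions are fixed before unblinding. loRMT and AllQual will follow PP.

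The cost is one word in each of two bullets, plus one sentence if the PP exclusion is kept. No new data are needed, and the planned 30 evaluable per group and 82.8% power are unchanged.

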## 3.3 Measurement Definitions

### 3.3.1 TMS Measures

Transcranial magnetic stimulation (TMS) is a neurophysiologic test for assessing upper motor neuron function. A magnetic coil is positioned on the head above the motor cortex at a location that causes excitation of the abductor pollicis brevis (APB) muscle in a participant's dominant hand. High-frequency sampling of motor evoked potentials (MEP) in the APB is used to record neurophysiologic response to specific magnetic field strengths and sequences. The MEP traces are used to calculate a range of derived measures. MEPs that were below the limit of detect and recorded as zero mV were replaced by 0.005 mV.

- Resting motor threshold (RMT): RMT is the magnetic field strength, measured as a percentage of the maximum stimulator output, that produces at least a 0.05 mV response in at least 5 of 10 consecutive trials.
- MEP amplitude: MEP amplitude is defined as the response when a stimulus equal to 120% of RMT is administered. MEP amplitude is calculated as the geometric mean of replicate estimates.
- Short-interval intracortical inhibition (SICI): Paired-pulse SICI is defined as the ratio of the response after a conditioning pulse equal to 80% of RMT is administered 3 ms prior to the signaling pulse divided by MEP amplitude. SICI is calculated as the geometric mean of replicate estimates.
- Intracortical facilitation (ICF): Paired-pulse ICF is defined as the ratio of the response after a conditioning pulse equal to 80% of RMT is administered 15 ms prior to the signaling pulse divided by MEP amplitude. ICF is calculated as the geometric mean of replicate estimates.
- Cortical silent period (CSP): CSP is the suppression of voluntary muscle contraction elicited by stimulation equal to 120% of RMT. CSP duration is measured from the time of the muscle activity suppression to return of muscle activity.
- Input/Output curve parameters: MEPs elicited by stimuli ranging in strength from 60% of RMT to 150% of RMT follow a sigmoidal curve with upper and lower thresholds and a smooth, symmetric transition between the thresholds. A four-parameter logistic function fit to the input/output curve after log-transformation of output potentials yields estimates of maximum amplitude, minimum amplitude, midpoint of activation, and slope at the midpoint of activation.

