- TMS quality: Good vs. poor quality TMS assessments will be evaluated as a measure of electrophysiologic response. Good quality will be defined as a central reader's evaluation that the TMS records were of good quality overall and that individual measurements of RMT, input/output curves, and CSP were of good quality.

TMS tracings were centrally reviewed and processed. Central readers indicated the reliability of the overall TMS assessment and of individual measures using a set of quality flags. Only TMS assessments that were evaluated as good quality overall and for measurement of RMT, input/output curves, and CSP are used for primary analysis. CSP times equal to zero were considered low quality whether flagged as such or not.

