### 3.8.2 Secondary Analyses of the Primary Efficacy Endpoint

Several secondary analyses will be investigated to assess sensitivity of our estimates of treatment effect to alternative modeling assumptions.

- Active vs. placebo: A secondary estimand of the efficacy of ezogabine will compare both 600 mg/day and 900 mg/day treatment arms vs. placebo, tested at alpha = 0.05. The following SAS code specifies the linear contrast for this comparison:

```
estimate "2|ActvsPlb|dAvg 6&8"
  post*ttrrnd*visit 2 2 0 -2 -2 0 -1 -1 0 1 1 0 -1 -1 0 1 1 0 / cl divisor=4;
```

- Random-slopes model: The visit-specific fixed effects will be replaced with a continuous predictor of month since treatment initiation. Data from Final Safety and Early Termination visits will be placed at their observed follow-up time. Only assessments completed through Week 10, the end of planned study drug exposure, will be included. The following SAS code specifies the model and the linear contrasts used to estimate treatment-dependent differences in rate of change per month:

```
proc mixed data=xxx method=reml;
  where visit in ("Screening","Baseline","Week 04","Week 06","Week 08","Week 10");
  class site id ttrrnd;
  model Value = month ttrrnd*month;
  random intercept / subject=site type=vc;
  random intercept month / subject=id(site) type=un;
estimate "2|600vsPbl|Slope/mn" intercept 0 month 0 ttrrnd*month -1 1 0 / cl;
estimate "2|900vsPbl|Slope/mn" intercept 0 month 0 ttrrnd*month -1 0 1 / cl;
estimate "2|ActvsPbl|Slope/mn" intercept 0 month 0 ttrrnd*month -2 1 1 / cl divisor=2;
```

- Shared-baseline mixed model with pMI for missing data: The shared-baseline mixed model with fixed effects for visits described above for the primary analysis will be applied to datasets generated by placebo multiple imputation (Ayele et al. 2014). Fifty imputed datasets will be generated for a given endpoint.
- PP sample: The primary efficacy model and the secondary random-slopes model and active vs. placebo estimand will be applied to the PP sample.
- loRMT sample: The primary efficacy model and the secondary random-slopes model and active vs. placebo estimand will be applied to the loRMT sample.

- AllQual sample: The primary efficacy model and the secondary random-slopes model and active vs. placebo estimand will be applied to the AllQual sample.

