### 3.8.3 Secondary Efficacy Endpoints

The key secondary efficacy endpoint of RMT will be analyzed using the same analysis samples and models as specified for the primary efficacy endpoint in Sections 3.8.1 and 3.8.2. Continuous non-key secondary efficacy endpoints and exploratory efficacy endpoints measuring electrophysiology and clinical progression will all be analyzed using the mITT sample and the primary efficacy analysis described in Section 3.8.1. Variables that are strongly right-skewed (e.g., MEP amplitude, ICF) will be log-transformed prior to analysis, and estimates will be back-transformed for reporting.

The binary indicator of good quality TMS recordings will be analyzed in an equivalent generalized mixed model treating the indicator variable as a Bernoulli random variable with logit link.

Weekly cramping frequency data will be analyzed in similar generalized mixed models treating the number of cramps experienced in a week as a negative binomial random variable with log link and with the log of the number of days at risk for cramps as an offset. Similarly, weekly number of days with fasciculations will be analyzed in similar generalized mixed models treating the number of days with fasciculations in a week as a binomial random variable with logit link. Because diary data are only collected after baseline, fixed effects in the model will include treatment group, post-baseline week, and baseline retrospective report of number of cramps experienced in the prior 30-day interval or the experience of fasciculations in the prior 14-day interval.

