### 3.8.6 Missing Data

Baseline values for efficacy endpoints will be determined from the last non-missing data collected prior to the first dose of study medication. The planned mixed model yields estimates that are unbiased conditional on the observed scores under a missing at random assumption. In addition, a secondary analysis of the primary endpoint will use placebo-based multiple imputation of missing data. Additional sensitivity analyses may be pursued to impute missing values or otherwise construct models for unobserved outcomes if more than 20% of participants are missing follow-up data for any reason.

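### The low-RMT sample drops visits by their own RMT value, so analysing RMT in it pulls a broadly constant drug effect on RMT toward zero

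*SAP*

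**What the plan says.** SAP 3.5 defines the loRMT sample as "ALS participants and observations in the PP sample with RMT less than 67% of maximum stimulator output" and gives the reason: "This criterion ensures that the full TMS input/output curve could be conducted". SAP 3.3.1 explains where the limit comes from: "MEPs elicited by stimuli ranging in strength from 60% of RMT to 150% of RMT follow a sigmoidal curve".

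SAP 3.8.2 lists analyses intended to "assess sensitivity of our estimates of treatment effect to alternative modeling assumptions". One of them is that the primary model, the random-slopes model and the active-versus-placebo contrast "will be applied to the loRMT sample". SAP 3.8.3 extends the whole set to the key secondary endpoint: "The key secondary efficacy endpoint of RMT will be analyzed using the same analysis samples and models as specified for the primary efficacy endpoint". It makes no exception for loRMT.

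Two other statements bear on the point. SAP 3.8.6 says: "The planned mixed model yields estimates that are unbiased conditional on the observed scores under a missing at random assumption". SAP 3.3.1 says: "Only TMS assessments that were evaluated as good quality overall and for measurement of RMT, input/output curves, and CSP are used for primary analysis".

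**The concern.** RMT is measured as a percentage of the stimulator's maximum output, so the filter and the endpoint are the same variable. The loRMT definition names observations as well as participants, which makes the cut apply visit by visit, after randomisation as well as before. A Week 6 or Week 8 RMT is discarded because of its own value. Missing at random allows dropout to depend on observed scores, but not on the score being removed.

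If the drug raises RMT, treated visits cross 67% more often than placebo visits and the highest treated values disappear. If it lowers RMT, the highest placebo values disappear. Either way the contrast shrinks.

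What is at stake is interpretation. A loRMT estimate of the RMT effect that lies nearer zero than the per-protocol estimate could be read as a sign of fragility when the cut alone would produce it. SAP 3.8.5 contemplates accepting RMT alone as evidence of benefit, so its supporting analyses would be read closely.

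**Working it through.** **1. The cut-off.** The curve runs to 150% of RMT and the stimulator cannot exceed 100%, so RMT can be at most 100 / 1.5 = 66.7%. At 67% the top stimulus would be 1.5 × 67 = 100.5%. The SAP's figure is reproduced. It is a limit on each session, which supports the visit-level reading: a pre-treatment cut could not guarantee the curve at Weeks 6 and 8.

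**2. Direction.** Let m(t) = E[Y | Y < t] for untreated RMT, c the cut and d a constant drug shift. The apparent effect after truncation is d − [m(c) − m(c − d)]. For a normal outcome the slope of m lies between 0 and 1, so the effect shrinks without changing sign.

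Example with assumed mean 60, SD 10 and d = +5:
- m(67) = 60 − 10 × 0.3123/0.7580 = 55.88.
- m(62) = 60 − 10 × 0.3910/0.5793 = 53.25.
- Apparent effect = 5 − (55.88 − 53.25) = 2.37, a ratio of 0.47.

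This compares post-treatment means only. The mixed model also uses pre-treatment values, which reduces the bias but does not remove it.

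**3. Size in the SAP 3.8.1 model, at trial size.** From the SAP: 40 per arm with 25% lost (3.4), 12 sites (2.3) and the model terms (3.8.1). Assumed, because the documents give no RMT figures: mean RMT 50, 55 or 60; between-person SD 8 or 12; within-person SD 4 or 7; site SD 3; slope SD 1 per month. Visits were Screening, Baseline, Weeks 6 and 8. Each simulated trial was fitted by REML to all visits and again to visits with RMT below 67. Loss is the paired difference in the Week 6/8 contrast against placebo.

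| Mean RMT | Loss for constant +6 (points) | Loss (%) | Loss / SE of the loRMT estimate |
|---|---|---|---|
| 50 | 0.55–1.14 | 9–19 | 0.5–0.7 |
| 55 | 0.90–1.87 | 15–31 | 0.75–1.1 |
| 60 | 1.30–2.58 | 22–43 | 1.0–1.5 |

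- The SE of the loRMT estimate was 1.08–1.93; the Monte Carlo SE of the loss for +6 was 0.04–0.14.
- Visits at 67 or more: 4–32% in placebo and 12–47% in the +6 arm.
- Constant −6: loss 0.17–2.07 points (3–35%). Constant +3: loss 0.23–1.09 points (8–36%).
- No effect: difference −0.21 to +0.06, within 2 Monte Carlo SE of zero in every scenario.
- With +6, the loRMT estimate fell below the full-data estimate in 85–97% of simulated trials, against 42–57% with no effect.

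**4. Size in large samples.** A separate fit with 60,000 per arm, without the site term, used assumed means of 50 to 65, between-person SD 8 to 12, residual SD 3 to 6, and shifts of 3 and 5 points in both directions.

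| Placebo Week 6 visits at 67 or more | Share of true effect retained |
|---|---|
| 2% | 0.96–0.98 |
| 11–13% | 0.83–0.90 |
| 26–31% | 0.69–0.82 |
| 40–44% | 0.58–0.78 |

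For example, with mean 60 and between-person, slope and residual SDs of 10, 1 and 4, a true +5 is estimated as +3.77. Every scenario showed attenuation and none changed sign.

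**5. Quality filter.** If reader grading already removes half of the sessions at 67 or more, the per-protocol versus loRMT gap for +6 is 0.34–2.15 points instead of 0.55–2.58. If it removes all of them the gap is zero, but the per-protocol and mITT samples are then truncated in the same way.

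**6. Non-constant effect.** With an average of +6 made up of +12 in the lower half of RMT and 0 in the upper half, the estimate changed by only −0.66 to +0.14 points over four scenarios.

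**The case against.** The strongest reply is that little depends on this. The key secondary test uses the mITT sample at 0.027 and has no explicit RMT cut. loRMT is one of several supportive analyses, and with no drug effect it shows no bias. That stands, and it is why the point is minor.

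The size is also open to challenge:
- At an assumed mean of 45 with SDs 8 and 4, about 1% of placebo visits reach 67, and a shift of +3 or +6 loses only 0.04–0.20 points (about 1–3%). The documents do not exclude this.
- The widest scenario includes implausible sessions. MEP amplitude and CSP need 120% of RMT, which is unattainable above 100 / 1.2 = 83.3%. In a simplified large-sample run at mean 60 with SDs 12 and 7, removing visits above 83.3 from the comparison cut the gap from 2.18 to 1.69.
- The loss-to-SE ratios assume the planned 40 per arm. SAP 3.7 reports slow enrolment and the final number is not given; a smaller trial has larger SEs and smaller ratios.
- The random-slopes model, also planned for loRMT, was not simulated.

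These points limit the size, not the direction. A looser reading, with participants selected once, would avoid the bias, but it does not fit the word observations or the stated purpose of the cut. The quality-filter argument does not rescue the analysis either. If reader grading removed every high-RMT session, loRMT would add nothing for RMT, and dropping RMT from loRMT would leave the truncation in mITT and per-protocol untouched. A separate loRMT sample suggests that not all such sessions are removed, but the documents do not say.

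**Conclusion.** The concern holds. As written, the loRMT analysis of RMT selects visits on the outcome being analysed. It is biased toward zero if the drug shifts RMT by a broadly constant amount and some visits reach 67%. An effect confined to low-RMT participants can offset most of the shrinkage.

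The size is unknown from the documents: negligible if few visits reach 67%, and up to 43% of a +6 effect in the most affected scenario simulated at trial size. A loRMT estimate of the RMT effect below the per-protocol estimate is therefore not evidence that the effect lacks robustness. Severity is minor, because no confirmatory conclusion rests on this analysis.

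**What to change.** In SAP 3.8.3, add one clause stating that RMT is not analysed in the loRMT sample. Leave the SAP 3.5 definition unchanged for SICI. This needs no new data and does not touch the mITT analysis of RMT.

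If a low-RMT check on RMT is wanted, add one sentence instead: for RMT only, select participants once by pre-treatment RMT below 67% and keep all their later per-protocol observations. Selecting on the mean of Screening and Baseline returned the full-data estimate to within 0.10 points for constant shifts of +6 and −6. Selecting on the Baseline value alone, in the large-sample fit, recovered 0.98–1.03 of the true effect. The sentence should name the value used and say what happens if a pre-treatment visit is missing or of poor quality; the last non-missing pre-dose value would match the baseline rule in SAP 3.8.6.

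The alternative has two costs. With selection on the Screening and Baseline mean, 6–25% of the kept post-baseline visits have RMT of 67 or more; the full curve cannot be run there, but that does not matter for estimating RMT. The SE is 2–22% larger than with all participants.
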